7.7.4 Signs/Symptoms of Local Irritation

At each study visit, beginning with Visit 1, subjects will be evaluated for any signs and symptoms of local irritation (application site reactions), including erythema, dryness, burning/stinging, erosion, edema, pain and itching. Each subject will be assigned a severity score by an Investigator based on the scale ranging from 0=Absent to 3=Severe.

Number and percentage of subjects with each severity will be presented by visit and by sign/symptom. Additionally, the shifts from baseline in irritation score will be tabulated by treatment, symptoms and scheduled post-baseline visits. The denominator for the proportions will be the number of subjects with any assessment of the sign/symptom both at baseline and at given visit.

7.7.5 Exposure to Product

The subjects will be instructed to use the diary to document all treatments administered, including the date and time and all treatments missed.

[REDACTED]

Number of missed doses will be calculated as follows. The number of doses missed in the dosing period (between the first and the last study drug application) will be taken directly from the CRF. [REDACTED]

[REDACTED]

[REDACTED] The compliance will be analyzed using

the descriptive statistics by treatment group. The proportion of compliant vs. non-compliant subjects will be tabulated for each treatment.

Duration of exposure will be calculated as Date of last use of study medication – Date of first use of study medication + 1. Duration of exposure will be summarized descriptively by treatment group.

Compliance and duration of exposure will be summarized for the Safety and mITT populations.

7.7.6 Exposure to Concomitant Medication

Concomitant medications and therapeutic treatments, including the use of sunscreen, OTC products, herbal products, topical and systemic medicines, dietary supplements and any current non-drug treatments/therapies will be assessed at the screening/baseline visit and at each subsequent study visit.

Medication or non-drug therapy will be classified as prior if the end date is known and is prior to the first use of the study medication. Medications and non-drug therapies that are ongoing or ended after the first use of the study medication will be classified as concomitant. If the end date of the medication or non-drug therapy is partially known so that there is an ambiguity whether it ended before or after the start of the study medication, the medication will be considered concomitant. If the end date is unknown, it will also be considered concomitant.

The concomitant medications will be summarized by treatment group, ATC class level 3 and preferred term as coded by the World Health Organization Drug dictionary March-2022 B3 and be listed in a by-subject listing. Prior medications will be listed only.

7.7.7 COVID-19 Screening

Temperature check and COVID-19 symptom (such as Stuffy or runny nose, Sore throat, Shortness of breath (difficulty breathing), Cough, Low energy or tiredness, Muscle or body aches, Headache, Chills or shivering, feeling hot or feverish (temperature check), vomiting, diarrhea, loss of sense of taste and smell) screening will be done for each subject at visit 1, 2, 3, 4 and Unscheduled / Early Discontinuation visit. During the screening, if the subject found to have any one of the above said symptoms, then it will be judged by the investigator whether

it is related or not-related to COVID-19 and appropriate procedures will be followed by the investigator and site. Results of the COVID-19 screening will be listed.

8. CHANGES FROM PROTOCOL-SPECIFIED ANALYSES

The definition of the mITT population was expanded in the SAP.

Otherwise, there are no changes from the protocol-specified analyses.

9. LIST OF PLANNED TABLES, FIGURES, AND LISTINGS

See separate document with the table, figure and listing shells.

11. APPENDICES

11.1 Study visit Schedule

Visit Number	Visit 1	Visit 2	Visit 3	Visit 4	Unscheduled/ Early Termination
Visit Day	Day 0	Day 28	Day 56	Day 84	
Visit Name	Baseline	Interim	Interim	End of Treatment	
COVID-19 symptom screening	X	X	X	X	X
Informed Consent	X				
Inclusion/Exclusion Criteria	X				
Demographics	X				
Medical History	X				
Physical Exam	X			X	X as needed
Vital Signs	X	X ³	X ³	X ³	X ³
Urine Pregnancy Test ¹	X	X	X	X	X
Clinical Assessment of Acne: Investigator's Global Assessment (IGA)	X	X	X	X	X
Investigator's Lesion Counts Inflammatory and Non-Inflammatory	X	X	X	X	X
Randomization	X				
Dispense IMP and Supplies	X	X ³	X ³		
Dispense Diary/Instructions	X	X	X		
IMP Review and Collection ⁴		X	X	X	X as needed
Subject Compliance/ Diary Review and collection		X	X	X	X as needed
Evaluation of Signs/Symptoms of Local Irritation (Application Site Reactions)	X	X	X	X	X
Adverse Event Assessment ²	X	X	X	X	X
Concomitant Medication Review	X	X	X	X	X

1 Tubal ligation is not considered equivalent to female sterilization. Women with a history of tubal ligation are still considered females of childbearing potential and must have a negative urine pregnancy test with a sensitivity of at least 25 mIU/ml hCG.

2 Any AEs reported after signing Informed Consent should be reported.

3 Only Temperature check at visit 2, 3, 4 and Unscheduled / Early Discontinuation as part of COVID-19 symptom screening.

4 Additional IMP and supplies will be provided to the Subject as required.

11.2 Code Fragments

ANOVA model for superiority analysis in the primary endpoint

```
proc glm data=<datasets name>;  
  by lesion_type;  
  class <treatment> <center>;  
  model <Percent change from baseline in lesion count at week 12> = <treatment> <center>  
  <treatment>*< center>/ ss3;  
  lsmeans <treatment> / pdiff cl;  
  output out=residuals residual=residual;  
run;  
quit;
```

Note: this analysis needs to be performed separately for test and reference treatments on a dataset containing only test and vehicle or reference and vehicle treatment subjects. If treatment-by-center interaction term is not significant at 0.05 level, the model will be rerun without this term.

Analysis of clinical equivalence in the primary endpoint

ANOVA model:

```
proc glm data=<datasets name>;  
  by lesion_type;  
  class <treatment> <center>;
```

```

model <Percent change from baseline in lesion count at week 12> = <treatment> <center>
<treatment>*<center>/ ss3;
lsmeans <treatment> / stderr;
output out=residuals residual=residual;

run;
quit;

```

Here dataset contains test and reference treatment subjects only.

Note: if the treatment-by-center interaction term is not significant at the 0.05 level, the model will be rerun without this term.

Fieller's method.

Generally, Fieller's formula allows to calculate the confidence interval for the ratio of two (possibly correlated) means of two samples a and b with expectations μ_a and μ_b , and variances $\nu_{11}\sigma^2$ and $\nu_{22}\sigma^2$ and covariance $\nu_{12}\sigma^2$. If $\nu_{11}, \nu_{12}, \nu_{22}$ are all known, then a $(1 - 2\alpha)$ confidence interval (mL, mU) for μ_a/μ_b is given by

$$(m_L, m_U) = \frac{1}{(1 - g)} \left[\frac{a}{b} - \frac{g\nu_{12}}{\nu_{22}} \mp \frac{t_{r,\alpha}s}{b} \sqrt{\nu_{11} - 2\frac{a}{b}\nu_{12} + \frac{a^2}{b^2}\nu_{22} - g \left(\nu_{11} - \frac{\nu_{12}^2}{\nu_{22}} \right)} \right]$$

where

$$g = \frac{t_{r,\alpha}^2 s^2 \nu_{22}}{b^2}.$$

Here s^2 is an unbiased estimator of σ^2 based on r degrees of freedom, and $t_{r,\alpha}$ is the α -level deviate from the Student's t-distribution based on r degrees of freedom.

In the case of this study the two samples are independent (different subjects), thus covariance can be assumed to be zero, and the formula simplifies to:

$$(m_L, m_U) = \frac{1}{1-g} \left[\frac{m_t}{m_r} \mp \frac{t_{r,\alpha}}{m_r} \sqrt{se_t^2 + \frac{m_t^2}{m_r^2} se_r^2 - g \cdot se_t^2} \right]$$

where

$$g = \frac{t_{r,\alpha}^2 se_r^2}{m_r^2}$$

Here m_t and se_t are mean and standard error estimate for test treatment and m_r and se_r for reference treatment correspondingly obtained from the above model. The degrees of freedom r can be obtained from the model as degrees of freedom for the error term in the overall ANOVA table, $\alpha = 0.05$ (for the 90% confidence interval). The term $t_{r,\alpha}$ can be calculated in SAS as `tinv(α , r)`.

Evaluation of skewness

This evaluation will be performed on the residuals output by the "output" statement in PROC GLM above:

```
proc univariate data=residuals;  
    var residual;  
run;
```

Non-parameteric rank ANOVA

If decision to use the rank ANOVA is taken, the data will be ranked first:

```
proc rank data=<dataset>  
    var <change_from_baseline>;  
    ranks rank;  
run;
```

After that the analysis will proceed using the same SAS code as described above but using rank variable instead of the original change from baseline.

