10.3.3.2 Test of Clinical Equivalence

The evaluations of clinical equivalence will be performed for the PP population.

For the primary efficacy assessment, the two-sided, 90% confidence interval on the test/reference ratio of the mean percent change from screening/baseline to week 12 in each lesion type will be calculated using Fieller's method and the pooled variance estimate (MSE) obtained from a two-way Analysis of Variance (ANOVA) of the Test and Reference results. The statistical model for the ANOVA will contain terms for treatment and center. If the skewness of the residuals from the ANOVA is outside of -2 to 2, then a nonparametric approach will be used to obtain the confidence intervals. Bioequivalence will be established if the 90% confidence intervals for the ratio of test/reference means, for both inflammatory and non-inflammatory lesion counts, are contained within the interval [0.80, 1.25] using the per protocol (PP) population.

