7.6.2.1 Analysis of clinical equivalence of test and reference treatments

To show the clinical equivalence, estimates of mean percent change from baseline in the inflammatory and non-inflammatory lesion counts will be calculated for the Test and Reference treatment, and then the 90% CI for the mean ratio will be constructed using Fieller's method. Bioequivalence will be established if the 90% confidence intervals for the

ratios of Test/Reference means are contained within the interval [0.80, 1.25] for the PP population for both lesion types (inflammatory and non-inflammatory).

To this end, first an ANOVA model will be fit (separately for each lesion type) with percent change from baseline in lesion count as outcome and treatment, center and treatment-by-center interaction as factors on the data from Test and Reference treatments only (excluding Vehicle subjects). If the treatment-by-center interaction factor is not significant at the 0.05 level, the model will be rerun without the interaction term. Treatment means and standard errors will be estimated from this model. Then Fieller's formula will be applied; covariance between the treatment means will be assumed to be 0. See [Appendix 11.2](#) for complete description of the Fieller's formula.

A non-parametric rank based ANOVA will be considered when the data is highly skewed. The evaluation of skewness, (using SAS[®] PROC UNIVARIATE) will be performed using the residuals from ANOVA and if the skewness statistic is less than -2 or greater than +2, the analysis will be performed on the ranks of the percent change in the inflammatory lesion count values.

Analysis of bioequivalence will be performed on the PP population

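### The bioequivalence interval sets the covariance of the two LS means to zero, which is wrong for the treatment + center model; with unequal centers the 90% CI is too wide and power is lost

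*SAP*

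**What the plan says.** Protocol 10.3.3.2 specifies a 90% Fieller interval for the Test/Reference ratio of mean percent change, using the pooled ANOVA variance, for each lesion type in the PP population. Both intervals must lie within 0.80 to 1.25. On the model it says: "The statistical model for the ANOVA will contain terms for treatment and center".

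SAP 7.6.2.1 and Appendix 11.2 first fit treatment, center and their interaction to Test and Reference subjects only. Then, "if the treatment-by-center interaction term is not significant at the 0.05 level, the model will be rerun without this term", which leaves the protocol's additive model. The means and standard errors come from PROC GLM with "lsmeans <treatment> / stderr".

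On the covariance, SAP 7.6.2.1 says that "covariance between the treatment means will be assumed to be 0". Appendix 11.2 prints the general Fieller formula with its covariance term v12, then removes the term with the reason: "In the case of this study the two samples are independent (different subjects), thus covariance can be assumed to be zero".

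**The concern.** Independent subjects make the two raw arm means independent. They do not make LS means from an additive model independent. Each LS mean is the equally weighted average of the estimated center effects plus a treatment effect, and the same center-effect estimates enter both. A small center, estimated imprecisely but given full weight, adds the same error to both arms. That error inflates both standard errors but largely cancels in a ratio near 1. The simplified formula counts the inflation and ignores the cancellation.

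This is the definitive equivalence test, and both lesion types must pass. An interval that is too wide can fail a truly equivalent product on either one. The SAP is also uneven: its superiority analysis takes the LS-mean difference from PROC GLM, which uses the model covariance, while the equivalence analysis fits the same kind of model and discards it.

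**Working it through.** **Inputs.** Model, LS means, zero covariance, 90% level and margins are from Protocol 10.3.3.2, SAP 7.6.2.1 and SAP Appendix 11.2. Sample size, means, SDs, allocation and the center-pooling rule are redacted, so there is no plan figure to reproduce. Assumed: 1:1 Test:Reference within centers, 20 centers, and the sizes, means and SDs stated below.

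**1. Covariance of the LS means.** Let center j hold n_j Test plus Reference subjects, with J centers and N = Σn_j. With a constant 1:1 split, the LS means are G + D/2 and G − D/2. G is the unweighted average of the center means and D the treatment difference, and the two are uncorrelated. Var(G) = (σ²/J²)Σ(1/n_j) and Var(D) = 4σ²/N. Hence:

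- Var = σ²[(1/J²)Σ(1/n_j) + 1/N] = (σ²/2J)(1/H + 1/A)
- Cov = σ²[(1/J²)Σ(1/n_j) − 1/N] = (σ²/2J)(1/H − 1/A)
- Correlation = (A − H)/(A + H)

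H cannot exceed A, and the two are equal only when all centers are the same size. These expressions agree with the direct matrix calculation L(X'X)⁻¹L'.

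**2. Effect on width.** At a ratio near 1 the Fieller variance is close to 2Var − 2Cov = 2σ²/(JA), whatever the spread of center sizes. With the covariance set to zero it is 2Var = (σ²/J)(1/H + 1/A). The standard error is therefore overstated by sqrt((A/H + 1)/2).

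**3. Worked example.** Take five centers each of 6, 10, 20 and 44 per arm, 400 per arm in all.

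- Σ(1/n_j) = 5(1/12 + 1/20 + 1/40 + 1/88) = 0.8485; divided by J² = 400 this is 0.002121. 1/N = 1/800 = 0.001250.
- Var/σ² = 0.003371, Cov/σ² = 0.000871, correlation 0.26.
- Overstatement: sqrt(0.003371/0.002500) = 1.16.
- With mean 50, SD 35 and observed ratio 1, the 90% interval is 0.910–1.099 with zero covariance and 0.922–1.085 with the model covariance. Equal centers also give 0.922–1.085.

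**4. Coverage and power.** Simulation of one lesion type: 20 centers, 320 per arm, mean reduction 55%. In the power columns the true ratio is 1. Paired entries are zero covariance / model covariance.

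| A/H | Correlation | SE overstated | Coverage, SD 50 | Power, SD 50 | Power, SD 40 | Pass rate at true ratio 0.80, SD 50 |
|---|---|---|---|---|---|---|
| 1.17 | 0.08 | 4% | 91% / 90% | 0.83 / 0.85 | 0.97 / 0.97 | 4.3% / 5.0% |
| 1.5 | 0.20 | 12% | 93% / 90% | 0.78 / 0.84 | 0.95 / 0.97 | 3.4% / 5.0% |
| 1.9 | 0.31 | 20% | 95% / 90% | 0.72 / 0.84 | 0.93 / 0.97 | 2.4% / 5.0% |
| 2.3 | 0.39 | 28% | 97% / 90% | 0.66 / 0.84 | 0.91 / 0.97 | 1.8% / 5.0% |

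At A/H = 1.9 the excess variance equals discarding 1 − 1/1.45 = 31% of the sample.

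**5. Where the result changes.** If the interaction is kept, each LS mean averages only its own arm's cell means; the covariance is exactly zero and the SAP formula is right. If the Test share p_j varies by center, Cov/σ² = (1/J²)Σ(1/n_j) − p̄(1 − p̄)/Σ n_j p_j(1 − p_j), which can be negative. For 20 centers of 40 with alternating 15:25 splits it is 0.001250 − 0.25/187.5 = −0.000083, and the interval is 1.6% too narrow.

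**The case against.** The algebra is not in dispute; the objections concern how much it matters.

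- **It is conservative.** With a steady allocation split the false-equivalence rate falls below 5%, so a passing result remains valid. This stands. The cost is power.
- **Pooling limits it.** SAP 7.6.1 pools small centers, and small centers drive A/H. In a check with 20 centers, 320 per arm and random center sizes, merging up to at least 8 per arm gave median widening of 2% to 8% as the coefficient of variation of center size rose from 0.3 to 1.0, and A/H never reached 1.9. With a minimum of 4 per arm, A/H reached 1.9 in 2.5% of draws at a coefficient of variation of 0.8 and in 21% at 1.0. This stands as a statement about likely size: the lower rows of the table need a weak pooling rule and strong imbalance. Nothing visible in the SAP makes pooled centers equal.
- **The power figures rest on assumptions.** This also stands. At SD 40 the losses are much smaller. The sample-size simulations may have used the planned zero-covariance interval, so a shortfall against planned power is not shown.
- **The direction is not guaranteed.** Near-equal centers with uneven splits, which PP exclusions can produce, make the interval slightly narrow. An extreme alternating 8:32 split raised the false-equivalence rate to 6.7%. This is a further reason to use the actual covariance.

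None of these supports the stated reason for zero covariance.

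**Conclusion.** The concern holds. In the additive model that the protocol specifies, and that the SAP reaches whenever the interaction is not significant, the two LS means are correlated unless the design is balanced. The planned primary interval is then not a 90% interval, and its miscalibration depends on the recruitment pattern. Under 1:1 splits the standard error is overstated by 4% at A/H = 1.17 and 28% at A/H = 2.3. At SD 50 and 320 per arm, this takes power for one lesion type from about 0.84 to between 0.83 and 0.66. With effective pooling the widening is probably in single digits. The size cannot be fixed from the documents, but the error in the stated rule does not depend on it.

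**What to change.** In Appendix 11.2, keep the general Fieller formula and take the covariance from the fitted model, for example by adding the `cov` and `out=` options to the equivalence LSMEANS statement. Confirm that the diagonal of that output equals the squared standard errors. Delete the zero-covariance statements in SAP 7.6.2.1 and Appendix 11.2 and replace the simplified formula. With c the estimated covariance and g unchanged:

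(1/(1−g)) · [ m_t/m_r − g·c/se_r² ∓ (t/m_r)·sqrt( se_t² − 2(m_t/m_r)c + (m_t²/m_r²)se_r² − g(se_t² − c²/se_r²) ) ]

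This reduces to the present formula when c = 0, so it also covers a retained interaction and balanced centers. The cost is a SAS option, two deletions and one replaced formula, with no added subjects or data. It should be made before unblinding, because a later change to the primary interval would look driven by the result.

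### SAP Appendix 11.2 drops BY lesion_type from the skewness and rank code, so the code as printed pools two endpoints that the SAP text analyses separately

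*SAP*

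**What the plan says.** Section 7.6.2.1 of the SAP (equivalence) says that "first an ANOVA model will be fit (separately for each lesion type"), takes skewness on the residuals from that ANOVA, and considers a rank-based ANOVA when the statistic falls outside −2 to +2. Section 7.6.2.2 (superiority) also treats the lesion types separately and applies the same condition. The protocol (10.3.3.2) is firmer: "If the skewness of the residuals from the ANOVA is outside of -2 to 2, then a nonparametric approach will be used".

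The calculation itself is in Appendix 11.2. Both PROC GLM fragments contain "by lesion_type" and the statement "output out=residuals residual=residual". The skewness step is introduced with "This evaluation will be performed on the residuals output by the 'output' statement in PROC GLM above" and begins "proc univariate data=residuals", with a VAR statement and no BY. The rank step begins "proc rank data=<dataset>", also without BY. It ends: "After that the analysis will proceed using the same SAS code as described above but using rank variable instead of the original change from baseline".

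**The concern.** A GLM run BY lesion type with a single output dataset puts inflammatory and non-inflammatory residuals into one file. PROC UNIVARIATE without BY then returns one skewness for the mixture, which belongs to no model in the plan. PROC RANK without BY ranks values of one endpoint against values of the other, so the rank analysis of each depends on the other's results.

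Both lesion types must have their 90% interval for the Test/Reference ratio inside [0.80, 1.25]. A wrong statistic feeding the method choice on either one can therefore affect the bioequivalence decision. It also leaves a programmer to choose between the code and the text when the definitive analysis is run.

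**Working it through.** **Code against text.**

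| Step | BY lesion_type in Appendix 11.2? | SAP text |
|---|---|---|
| ANOVA | Yes | Separate by lesion type (7.6.2.1, 7.6.2.2) |
| Skewness | No | Residuals from the ANOVA; per type not stated |
| Ranking | No | 7.6.2.1 names only inflammatory counts |
| ANOVA on ranks | Yes (same code) | Not detailed |

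**What pooling does to skewness.** The plan states no figure to reproduce: N, means and SDs are redacted. ANOVA residuals average zero within each lesion type. With equal numbers per type, let k = SD1/SD2 be the ratio of residual SDs and g1, g2 the two skewnesses. Then

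pooled skewness = [(k³·g1 + g2)/2] / [((k² + 1)/2)^1.5].

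With type 2 symmetric (g2 = 0):

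- k = 1: 0.5/1 = 0.50·g1, so g1 must exceed 4.0 for the pooled value to pass 2
- k = 1.5: 1.688/2.072 = 0.82·g1 (threshold 2.46)
- k = 2: 4/3.953 = 1.01·g1 (threshold 1.98)
- k = 3: 13.5/11.18 = 1.21·g1 (threshold 1.66)
- k = 0.67: 0.24·g1 (threshold about 8.2)

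The pooled value can also pass 2 when neither type does. With g1 = g2 = 1.8 and k = 2 it is 8.1/3.953 = 2.05.

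A simulation with an assumed 300 per arm, gamma errors for type 1 and normal errors for type 2 agrees. With g1 = 3, the symmetric type is moved to ranks in 9% of runs at equal SDs, 75% at k = 1.5 and 98% at k = 2. At equal SDs the skewed type is masked in 91%.

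**Illustrative size.** Assumptions:

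- 200–400 per arm, no center effect, lesion types independent
- inflammatory count ratio lognormal with mean 0.5 and log-SD s
- non-inflammatory change normal, 45% mean reduction on Reference, SD 30 or 40
- a switch to ranks whenever pooled |skewness| > 2

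The inflammatory SD is 50·√(e^(s²) − 1) and its skewness is (e^(s²) + 2)·√(e^(s²) − 1). Putting these into the formula above gives the third column. The last two columns are simulated, with 1,000 trials per setting (standard error at most √(0.25/1000) = 1.6 points).

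| s | Inflammatory SD; skewness | Pooled skewness, other SD 30 / 40 | Symmetric type moved to ranks | Non-inflammatory declared equivalent at true ratio 0.80 |
|---|---|---|---|---|
| 0.6 | 32.9; 2.26 | 1.29 / 0.82 | about 0–8% | about 5–9% |
| 0.7 | 39.8; 2.89 | 2.08 / 1.43 | about 9–35% | about 11–34% |
| 0.8 | 47.3; 3.69 | 3.14 / 2.33 | about 33–83% | about 27–72% |

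On means, the last column would be 4–6%. The non-inflammatory type's own skewness never left ±2. The last column ranks percent change; ranking percent reduction instead gives about 12–26% at s = 0.8. In the masking direction, at s = 0.6 the inflammatory type's own skewness exceeds 2 in about 45–58% of trials, while the pooled value does so in 0–8%.

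**How much is due to BY.** For means −40 and −50 with SD 30 (ratio 0.80), the ratio of mean ranks is about 1.21 with BY and 1.185 to 1.24 without, depending on the other type's mean. All lie inside 1.25. Ranking the non-inflammatory type with BY in every trial still declares equivalence in about 22–77%. Much of the excess therefore comes from applying Fieller's ratio and [0.80, 1.25] to ranks.

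**The case against.** The strongest reply is that this is template code. The appendix offers fragments with placeholders; the rank step even names change from baseline where the endpoint is percent change. A programmer must complete it, guided by 7.6.2.1 and 7.6.2.2, which separate the lesion types. Section 7.6.2.1 names only inflammatory counts for ranking, which does not fit a joint ranking. The SAP says that ranks will be considered, so no statistic forces the switch.

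A reader might therefore infer too much: that the SAP has adopted one pooled skewness as the rule for both endpoints, or that false equivalence on the order of 27–72% is to be expected. The documents support neither. Pooling appears only in the code, the switch is discretionary in the SAP (though not in the protocol), and those rates belong to the most skewed of three assumed settings.

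The scenario is also stylised. The same subjects supply both counts, so independence is unlikely. A normal with mean −45 puts about 8% of Reference values below −100% at SD 40 (z = −55/40 = −1.375) and about 3% at SD 30, which a lesion count cannot reach.

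These points limit the size but do not remove the defect. The appendix is the only place that shows how skewness and ranks are computed, no sentence states the rule per lesion type, and discretion informed by the wrong statistic is still misinformed.

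**Conclusion.** Wrong as written: the printed code contradicts the separate-by-type analysis in the SAP text, and the text does not state the rule clearly enough to override it. Literal execution errs in two directions. It masks skewness when SDs are similar, and it moves a symmetric endpoint to ranks when the skewed type has the larger residual spread.

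The practical size is unknown because N and SDs are redacted. Under the stated assumptions, the effect on false equivalence is small at log-SD 0.6 and large at 0.8, and part of it is a separate weakness of the rank interval that BY does not repair. No effect of masking on the decision has been shown; masking leaves the endpoint on its ratio-of-means test. If neither type is clearly skewed, the effect is usually nil.

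**What to change.** In Appendix 11.2, add `by lesion_type;` to PROC UNIVARIATE and PROC RANK, with the data sorted by lesion type. In 7.6.2.1 and 7.6.2.2, state that skewness is assessed and the method chosen separately for each lesion type and each treatment comparison, so that only the type that triggers the rule leaves the mean-based ANOVA. In 7.6.2.1, reword the ranking sentence so that it covers whichever lesion type triggers the rule, not inflammatory counts alone.

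The cost is two lines of code and short text edits, with no new data and no protocol amendment. The use of a ratio margin on ranks needs its own resolution.

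### The skewness and ranking code in SAP 11.2 omits the split by lesion type that SAP 7.6.2.1 and 7.6.2.2 require

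*SAP*

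**What the plan says.** **Text.** SAP 7.6.2.1 fits one ANOVA per lesion type for equivalence. SAP 7.6.2.2 does the same for superiority and applies the rank option under the same circumstances. The trigger is the skewness of the ANOVA residuals: ranks are used "if the skewness statistic is less than -2 or greater than +2". Protocol 10.3.3.2 and 10.3.3.3 and SAP 5 also tie the rule to the ANOVA residuals. On what is ranked, SAP 7.6.2.1 says "the analysis will be performed on the ranks of the percent change in the inflammatory lesion count values". It has no matching sentence for the non-inflammatory count.

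**Code.** In SAP 11.2 both PROC GLM fragments contain "by lesion_type" and the line "output out=residuals residual=residual". The skewness fragment is introduced as working on those residuals. It reads "proc univariate data=residuals", followed only by a VAR statement. The ranking fragment starts "proc rank data=<dataset>" and has only VAR and RANKS; its VAR placeholder is `<change_from_baseline>`. The ranks then return to the earlier code: "After that the analysis will proceed using the same SAS code as described above but using rank variable".

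**The concern.** The -2/+2 rule decides how each co-primary endpoint is analysed, and both endpoints must succeed for equivalence and for superiority. The text leads to one skewness value per lesion type. The printed code gives a single value for the two types together.

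If the code were followed literally, marked skewness in one lesion type could be diluted by the other and missed. It could also push the other type onto ranks without cause. Ranks computed across both types would place each subject's inflammatory result on a scale shared with non-inflammatory results. A programmer who has to choose between code and text is choosing part of the primary method, and a correction made after unblinding could look data-driven.

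**Working it through.** No figure in the documents depends on this point, so there is none to reproduce. The sample-size assumptions are redacted and are not needed.

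**1. Tracing the code**

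- PROC GLM with a BY statement needs data holding both lesion types, and its OUTPUT statement writes both sets of residuals to the one dataset `residuals`.
- PROC UNIVARIATE on that dataset without BY returns one skewness for the mixture.
- PROC RANK without BY assigns one run of ranks over everything in its input. The ranks are fed back into code that runs by lesion type, so that input must hold both types.

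**2. Code against text**

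| Step | SAP 7.6.2.1 / 7.6.2.2 | SAP 11.2 as printed |
|---|---|---|
| ANOVA | separate per lesion type | BY lesion_type |
| Skewness check | residuals of that ANOVA | both types together |
| Ranking | percent change; inflammatory count named | both types together; placeholder says change |

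Change and percent change can order subjects differently. A fall from 20 to 10 lesions is -10, or -50%. A fall from 60 to 40 is -20, or -33%.

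**3. What pooling does to the skewness value**

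All skewness values and SDs here are assumptions. Residuals average zero within each lesion type, and each type is taken to have the same number of subjects. With skewness g1, g2 and residual SDs s1, s2:

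pooled skewness = [(g1·s1³ + g2·s2³)/2] / [(s1² + s2²)/2]^1.5

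*Other type symmetric (g2 = 0), k = s1/s2.* The pooled value is g1 times (k³/2)/[(k²+1)/2]^1.5.

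| k | Factor | g1 needed for a pooled value of 2 |
|---|---|---|
| 0.5 | 0.126 | 15.8 |
| 1 | 0.500 | 4.0 |
| 1.5 | 0.815 | 2.5 |
| 2 | 1.012 | 2.0 |

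*Both types equally skewed (g1 = g2).* The factor is [(k³+1)/2]/[(k²+1)/2]^1.5. It is 1.00 at k = 1 and 4.5/3.953 = 1.14 at k = 2; k = 0.5 also gives 1.14. Nothing is masked.

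*Intermediate cases.*

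| g1 / g2 | s1 / s2 | Pooled | Consequence |
|---|---|---|---|
| 2.5 / 0.5 | 30 / 30 | 1.50 | breach in the first type missed |
| 3.0 / 0.5 | 30 / 40 | 1.28 | breach in the first type missed |
| 3.0 / 0.5 | 45 / 30 | 2.56 | second type also moved to ranks |
| -2.5 / +2.5 | 30 / 30 | 0.00 | both breaches missed |

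**4. Simulation**

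Assumptions: 300 per arm, 10 centers, shifted-gamma errors, treatment-plus-center ANOVA per type, 300 runs per scenario.

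- Skewness 3 / 0.3, SD 30 / 30: the pooled check missed the inflammatory breach in 87% of runs.
- Skewness 3 / 0.5, SD 30 / 40: missed in 98%.
- Skewness 3.5 / 1, SD 50 / 30: the type that did not breach was sent to ranks in 100%.

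For the ranks themselves, in one simulated Test-Reference dataset the inflammatory 90% Fieller interval on mean ranks was 1.162 to 1.357 by type and 1.091 to 1.271 pooled. Both upper limits exceed 1.25, so the conclusion was the same. In another simulated dataset with equal arms, the non-inflammatory intervals were almost identical: 0.944 to 1.103 by type and 0.944 to 1.100 pooled. In a simulated superiority dataset the inflammatory p-value was 9e-17 by type and 8e-11 pooled; the non-inflammatory values were 2.3e-4 and 6.7e-5. Pooling changed the numbers but not the conclusion in these datasets.

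**The case against.** The strongest reply is that the text already settles the matter: one ANOVA per lesion type means one residual set and one skewness value per type. On that view SAP 11.2 holds only sketches. They use angle-bracket placeholders, the PROC RANK line as printed lacks a semicolon (possibly an effect of reading the PDF), and both GLM fragments write to the same dataset name. A programmer following 7.6.2.1 would add the BY statement.

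Most of this stands. A reader might infer from the code that the plan is to pool the two lesion types. The documents do not support that, since no sentence in either one describes pooling and the analysis sections say the opposite. A reader might also infer that the ranked analysis is meant to use a different endpoint. That is not supported either: 7.6.2.1 speaks of percent change, and the GLM code into which the ranks are fed has percent change as its response. The placeholder is probably loose labelling.

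The reply does not close the gap on ranking, however. The one sentence describing the ranks names only the inflammatory count, so for the non-inflammatory endpoint the fullest instruction is the code, and the code mixes the types.

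On size, the triggers of 4.0 and 15.8 need the other lesion type to have no skewness at all. Percent change is bounded below at -100% and has no such upper bound for either type, so long tails in the same direction are plausible, and then little is masked.

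**Conclusion.** The conflict is real. SAP 7.6.2.1 and 7.6.2.2 call for a decision per lesion type; the skewness and ranking fragments in SAP 11.2 would give one pooled decision and mixed ranks if run literally. The ranking variable and its application to non-inflammatory counts are also not cleanly specified.

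The effect is conditional on literal use of the fragments and on how differently the two lesion types are distributed. With one type symmetric and equal SDs, the working threshold for the other rises from 2 to 4. With equal skewness in both, the pooled value is 1.00 to 1.14 times the common value for SD ratios between 0.5 and 2. These figures rest on assumed skewness and SDs and on equal numbers per type. They show what could happen; they are not an estimate for this trial. The documents give no basis for saying that the trial's conclusion would change.

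The point is worth correcting because the rule selects the primary method and the correction has no drawback. It does not call the design into question.

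**What to change.** - In SAP 11.2, add `by lesion_type;` to PROC UNIVARIATE and to PROC RANK, with the data sorted by lesion type.
- Replace the ranking placeholder with percent change from baseline in lesion count at Week 12.
- In SAP 7.6.2.1, state that the skewness rule and the ranking apply separately to inflammatory and non-inflammatory counts and to each two-arm comparison. SAP 7.6.2.2 then inherits this through its existing cross-reference.
- While editing, complete the PROC RANK line and give each GLM run its own residual dataset name, so that each check reads the residuals of its own comparison.

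The cost is two code lines, one variable name and one sentence. Conduct and sample size are unaffected. The change should be made before unblinding. It does not address whether a ratio of mean ranks can be judged against [0.80, 1.25], which is a separate question.
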